4.2 Intervention

Study Periods

Each subject will undergo 3 periods (screening, treatment, and post-study follow-up).

Screening

The screening period will be from the signing of the informed consent until the first dose of the first study drug on Day 1 of Cycle 1 (C1D1). The screening period should not exceed 28 calendar days before C1D1.

Treatment

A treatment cycle lasts 28 days. The treatment period will be from the first dose of the first study drug until the last dose of the last study drug.

The treatment will continue until the disease progression, death, unacceptable toxicity, withdrawal of consent, or another reason for permanent discontinuation of treatment.

Patients with documented progression of disease may be allowed to continue on study if the patient is tolerating treatment, and in the opinion of the investigator, the patient is deriving clinical benefit from continuing study treatment and continuation of treatment is approved by the principal investigator. If said patient continues treatment post progression, they will require reconsent.

Dose levels of mirdametinib are summarized in section 10.2.

Post-study Follow-up

The post-study follow-up will include the end of treatment (EoT) visit, the safety follow-up visit, and the long-term follow-up.

An End of Treatment (EoT) visit will be performed within 7-14 days after the administration of the last dose of the last study drug.

The safety follow-up (FU) visit will be performed 30 days after the last dose of the last study drug treatment (except for subjects who died, withdrew consent, and objected to further data collection or were lost to follow up). The safety FU assessment can be done via the clinic visit (recommended) or via a phone call (if subject cannot attend the clinic visit or has started a new anti-cancer treatment). The investigator may order unscheduled FU visits after the 30-day safety FU visit if the adverse events ongoing at the safety FU are deemed to be clinically significant and related to the study drug(s).

The long-term follow-up will aim to obtain the information necessary for the duration of response (DOR) and the progression-free survival (PFS) endpoints. The long-term follow-up visits will be performed via clinic visit or phone call about every 3 months for 12 months

Memorial Sloan Kettering Cancer Center
[name]
[name]

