13.4.2 Timing of Radiographic Evaluations

All patients will undergo serial radiographic assessments to assess tumor response. Initial tumor imaging at screening must be performed within 28 days prior to the date of the first dose of study drug. Scans performed prior to the signing of the ICF as part of routine clinical management are acceptable for use as initial tumor imaging if they are of diagnostic quality and performed within 28 days prior to the date of first dose.

Memorial Sloan Kettering Cancer Center
[name]
[name]

Radiographic evaluations to assess extent of disease will be conducted at screening and every 8 weeks (56 ± 5 days) from Cycle 1 Day 1 for the first 12 cycles on study (or sooner if clinically indicated). Thereafter tumor assessments will be performed every 12 weeks (84 ± 7 days). Per RECIST v1.1, CR or PR should be confirmed; tumor imaging for confirmation of response must be performed at least 4 weeks after the first indication of response.

Imaging should not be delayed for delays in cycle starts or extension of combination treatment cycle intervals.

Radiographic evaluations will continue until PD, start of alternate anticancer therapy, withdrawal of consent to study participation, becoming lost to follow-up or death. If a patient discontinues treatment for a reason other than radiographic disease progression, withdrawal of consent to study, lost to follow-up, or death, scans should continue at the specified intervals until progression is confirmed or until the start of subsequent anticancer treatment.

If a patient discontinues treatment for clinical progression and does not meet RECIST v1.1 criteria for progression, scans should continue at the specified intervals until progression is confirmed or until the start of subsequent anticancer treatment.

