14.5 Efficacy Analyses

The primary efficacy analyses will be performed using the Efficacy Population.

Efficacy endpoints will be based on RECIST v1.1 by investigator's assessment:

- **Objective Response Rate (ORR)** is defined as the proportion of patients with confirmed CR or PR (i.e., 2 visit responses of either CR or PR at least 4 weeks apart) according to RECIST v1.1 criteria.
 - The maximum percent reduction in tumor size will also be presented as a waterfall plot.
- **Clinical Benefit Rate (CBR)** is defined as the proportion of patients with a confirmed best response of CR or PR, or SD that is sustained for at least 4 months after the first dose of mirdametinib according to RECIST v1.1 criteria.

- **Duration of Response (DOR)** (applicable only to patients with confirmed CR or PR) is defined as the time interval between the date of the earliest qualifying response (CR or PR) and the date of disease progression or death for any cause, whichever occurs earlier.
 - For patients who are alive without disease progression following response, DOR will be censored on the date of last evaluable tumor assessment or last follow-up for disease progression.
- **Progression-Free Survival (PFS)** is defined as the time from the first day of study drug administration (Day 1) to disease progression as defined by RECIST v1.1 criteria, or death from any cause.
 - Patients who are alive and free from disease progression will be censored at the date of their last tumor assessment.

For ORR and CBR, patients without a post-baseline tumor assessment will be excluded as they are not efficacy evaluable. The ORR and CBR calculation will include only efficacy evaluable patients.

An exact binomial 95% confidence interval for CBR and ORR will be calculated in each treatment group using the Clopper-Pearson method.

For PFS, Kaplan-Meier curves will be generated, and the median time-to-event and the associated 95% CIs will be provided. In addition, the rate of PFS at 6 months will be derived from the corresponding Kaplan-Meier curves and the associated 95% CIs calculated using Greenwood's formula on the $\ln[-\ln(\text{survival scale})]$ and back transformed. This analysis will include the patients in the efficacy population.

Depending on responses seen, a central review of all images may also be performed by an independent reviewer as a sensitivity analysis.

Sample size justification and patient numbers.

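### DOR has two alternative censoring dates, one of which can be a phone contact without imaging, while PFS has one; DOR may be overstated and can exceed the same patient's PFS

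*Combined protocol and SAP*

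**What the plan says.** Section 14.5 (Efficacy Analyses) bases the efficacy endpoints on investigator-assessed RECIST v1.1. It defines DOR as "the time interval between the date of the earliest qualifying response (CR or PR) and the date of disease progression" or death, whichever is earlier. PFS "is defined as the time from the first day of study drug administration (Day 1) to disease progression" or death. The closing events are therefore the same and only the starting dates differ.

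The censoring rules are not the same:

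- DOR: "DOR will be censored on the date of last evaluable tumor assessment or last follow-up for disease progression". Nothing says which date takes precedence.
- PFS: "Patients who are alive and free from disease progression will be censored at the date of their last tumor assessment".

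Four other sections determine what a follow-up date can be:

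- Section 4.2: "The long-term follow-up will aim to obtain the information necessary for the duration of response (DOR) and the progression-free survival (PFS) endpoints", and "The long-term follow-up visits will be performed via clinic visit or phone call about every 3 months for 12 months" after the last dose. A footnote to the Schedule of Assessments also allows telehealth.
- Section 11.10 describes the same visits as being for safety.
- Section 13.4.2 sets scans "every 8 weeks (56 ± 5 days) from Cycle 1 Day 1 for the first 12 cycles on study" and keeps them going after treatment stops, until progression is confirmed or other anticancer treatment begins.
- Section 11.8 follows a patient who needs other anticancer treatment by visit or phone every 12 weeks for up to a year.

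Section 14.5 has no censoring rule for new anticancer therapy, for either endpoint.

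**The concern.** A response lies inside the progression-free interval, so a patient's DOR should never be longer than that patient's PFS. Two censoring rules for the same event allow exactly that.

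A call cannot establish RECIST status. If the call date is used, the unscanned months are credited as continued response. For a responder who has moved to another drug, that time may reflect the later drug and not mirdametinib. Because the text offers two dates and no rule, the choice could be made after the data are seen, in an open-label trial with investigator-assessed response. What is at stake is the credibility of the DOR summary and its consistency with PFS.

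**Working it through.** The documents give no DOR or PFS figure for this point, so there is nothing to reproduce. The check is date arithmetic, followed by two illustrations under assumed inputs.

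**Formulas, counting days from Day 1, for a responder censored alive without progression**

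- PFS = last scan
- DOR by scan = last scan − first response
- DOR by call = last follow-up − first response
- DOR by call exceeds PFS exactly when (last follow-up − last scan) > first response

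**Example patient**

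Inputs from the plan:
- Scans every 56 days (13.4.2), so the earliest scheduled response is at about day 56.
- For confirmation, "tumor imaging for confirmation of response must be performed at least 4 weeks after the first indication of response"; the day-112 scan satisfies this.
- Calls about every 3 months for 12 months after the last dose (4.2).

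Assumptions:
- The last scan and last dose are both at day 168.
- The patient then starts new therapy without documented progression, or misses all later scans.
- The patient is alive at the 12-month call, at day 168 + 365 = 533.
- Quarterly calls fall at +91, +182, +273 and +365 days.

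Results:
- PFS = 168 days
- DOR by scan = 168 − 56 = 112 days
- DOR by 12-month call = 533 − 56 = 477 days
- DOR by the earlier calls = 168 + 91 − 56 = 203, 168 + 182 − 56 = 294, and 168 + 273 − 56 = 385 days

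DOR already exceeds PFS at the first call, because 91 > 56.

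**Later responses.** By the same inequality, a response at day 112 or 168 gives DOR > PFS from the second call (182 days), one at day 224 from the third (273 days), and one at day 280 at the fourth (365 days).

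**Direction and size.** Moving a censoring date later without adding events can never lower a Kaplan-Meier estimate. A simulation of 40,000 responders assumed a true median DOR of 6 months, with 10% to 40% of patients stopping scans without progression:

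| Progression found at calls | 12-month DOR, call rule | 12-month DOR, scan rule |
|---|---|---|
| none | 0.31 to 0.38 | about 0.28 |
| half (chance per call) | 0.29 to 0.32 | about 0.28 |
| all | 0.28 to 0.29 | about 0.28 |

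The simulated median was 7.4 months under both rules in every scenario.

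**Few responders.** Take five responders, with assumed events at 4, 6, 8 and 10 months and one censored.
- Censored at 1.8 months (scan), the curve is 3/4 = 0.75 at month 4, then 0.75 × 2/3 = 0.50 at month 6. The median is 6 months.
- Censored after month 10 (call), the curve is 0.80, 0.60 and 0.40 at months 4, 6 and 8. The median is 8 months.

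**After the fix.** With scan censoring for both endpoints, DOR = PFS − time to first response for every censored responder, so DOR cannot exceed PFS.

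**The case against.** The strongest reply is that the follow-up wording sits under a RECIST v1.1 heading, and Section 13.4.3 makes RECIST the measure for the date of progression. On that reading it means a contact at which progression was properly assessed. Section 11.10 supports this by calling the late visits safety visits. The reading is possible, but Section 4.2 ties the visit-or-phone follow-up directly to DOR and PFS, so a contact without imaging remains a permitted date. The two descriptions of these visits show that the text does not settle the matter.

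The second reply concerns scope, and it stands. Scans do not stop when treatment stops (13.4.2). Section 11.8 says other anticancer treatment should wait for documented progression, although it provides for a patient who needs it sooner. Patients lost to follow-up, or who withdraw and object to further data collection, have no long-term contacts. The affected group is therefore narrow, and the 12-month call is close to the worst case.

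A reader might also infer that reported DOR will be overstated. The documents do not support this: it happens only if the follow-up date is used and progression goes undetected at the contacts. If the analyst takes the last scan, nothing is inflated.

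**Conclusion.** The point holds as a conflict between two stated censoring rules, one of which is ambiguous. Section 14.5 permits a DOR censoring date without tumor assessment, and using it can give a DOR longer than the same patient's PFS: 477 against 168 days in the example, where scan censoring gives 112. This rests on the follow-up option being used, on the patient starting new therapy without documented progression or missing scans, and on no progression being recorded at the contacts.

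Two stronger inferences should be resisted. One is that the median DOR would shift. Section 14.5 names Kaplan-Meier and a median for PFS only, and the large simulation showed movement in the 12-month tail and not in the median. With about five responders a single patient can move a median, as from 6 to 8 months above, but that shows what is possible and is not a forecast. The other is that a cohort's verdict is at risk. It is not: the criterion counts responses (at least 5 of 28), and DOR plays no part in it.

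DOR is a secondary, descriptive endpoint. The correction should still be made, because the rule as written can yield a logically impossible result and the remedy is only text.

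**What to change.** In Section 14.5, delete the follow-up alternative from the DOR censoring sentence, so that DOR is censored at the last evaluable tumor assessment, as PFS is. Add one sentence covering both endpoints: patients who start new anticancer therapy without progression are censored at the last evaluable assessment before that therapy. The deletion alone would align the two dates but leave the main route unaddressed, since a progression or death recorded after new therapy would still count in both endpoints.

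The change needs no extra patients, visits or scans. Its cost is that reported DOR may be shorter. For an affected patient the difference can be large (112 instead of 477 days in the example); if few patients are affected, the change in the summary should be modest.

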 - b. If 1 of the first 3 evaluable subjects in Dose Level -2INT exhibit a DLT in Cycle 1, then a sufficient number of subjects will be treated with mirdametinib 2 mg BID PO, intermittently dosed, in combination with the recommended dose of fulvestrant to accrue 6 evaluable subjects.
 - c. If ≤ 1 of 6 evaluable subjects in Dose Level -2INT exhibit a DLT in Cycle 1, then **mirdametinib 2 mg BID PO**, intermittently dosed, will be declared as the recommended dose for Part 2 (RP2D) in combination with fulvestrant.
 - d. If ≥ 2 of the first 3 evaluable subjects or ≥ 2 of the 6 evaluable subjects in Dose Level -2 exhibit a DLT in Cycle 1, then the Arm 1 will be discontinued. The reason for discontinuation of Arm 1 will be that 2 mg BID PO, dosed intermittently, is deemed to be the minimum dose required for sufficient clinical benefit from mirdametinib in combination with fulvestrant in the refractory metastatic breast cancer.

Arm 1 - Part 2 (Expansion Cohorts)

The following expansion treatment groups (up to 28 subjects each). Both cohorts are planned and the rationale for sample size is included in section 14.5. These will initially be started, either in parallel or sequentially depending on the results of Part 1:

Memorial Sloan Kettering Cancer Center
[name]
[name]

1. Subjects with hormone receptor-positive, HER2-negative metastatic breast cancer exhibiting NF1 loss defined as homozygous deletion of NF1 by NGS assay; truncating or nonsense mutations in NF1; OncoKB defined pathogenic missense mutation; OncoKB defined activating mutation in KRAS or HRAS.
2. Subjects with hormone receptor-positive, HER2-negative metastatic breast cancer exhibiting EGFR amplification defined as >1.9 copies of EGFR by NGS assay; ERBB2 hotspot somatic mutation defined as activating by OncoKB.

The above expansion treatment groups are prioritized for this study, however as an exploratory treatment group to be considered in the future is the following cohort:

1. Subjects with hormone receptor-positive, HER2-negative metastatic breast cancer exhibiting OncoKB defined activating mutations in BRAF, CRAF, or MEK1/2

Arm 2 – Part 1 (Dose escalation of mirdametinib as single agent)

Part 1 will be conducted in three sequential Dose Level escalations according to the 3+3 design based on the incidence of dose-limiting toxicities (DLT) and the overall safety profile of the study treatments. The DLT definitions are listed in [Section 15.3](#).

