- d. If ≥ 2 of the first 3 evaluable subjects or ≥ 2 of the 6 evaluable subjects in Dose Level 2 exhibit a DLT in Cycle 1, then **mirdametinib 4 mg BID PO** given continuously will be declared as the recommended dose for Part 2 (RP2D).

6. Dose Level 3 (Dose Level escalation **8 mg BID PO** given continuously)

- a. Up to 3 subjects will be treated with mirdametinib as a single agent at the dose of **8 mg BID PO** in Dose Level 3
- b. If ≤ 1 of the first 3 evaluable subjects in Dose Level 3 exhibit a DLT in Cycle 1, then a sufficient number of subjects will be treated with mirdametinib **8 mg BID PO** given continuously to accrue 6 evaluable subjects.
- c. If ≤ 1 of 6 evaluable subjects in Dose Level 3 exhibit a DLT in Cycle 1, then **mirdametinib 8 mg BID PO** given continuously will be declared as the recommended dose for Part 2 (RP2D).
- d. If ≥ 2 of the first 3 evaluable subjects or ≥ 2 of the 6 evaluable subjects in Dose Level 3 exhibit a DLT in Cycle 1, then **mirdametinib 6 mg BID PO** given continuously will be declared as the recommended dose for Part 2 (RP2D).
- e. The dose of mirdametinib as single agent will not be escalated above **8 mg BID PO** given continuously.

Arm 2 – Part 2 (expansion cohorts for mirdametinib as single agent)

One or more expansion cohorts (up to 30 subjects each) will be started, either in parallel or sequentially depending on the results of Part 1. The purpose will be to evaluate the efficacy and safety of the RP2D of mirdametinib as single agent (as determined in Part 1 of Arm 2) in the subjects with advanced solid cancers (with the exception of colorectal, small bowel, biliary and ampullary cancers) harboring activating mutations in MEK1/2.

Memorial Sloan Kettering Cancer Center
[name]
[name]

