14.0 BIOSTATISTICS

14.1 Analysis Populations

The following analysis populations will be used:

- **DLT Evaluable Population** consists of patients who receive at least 80% of planned total doses of mirdametinib in cycle 1 (in Arm 1 only, also both doses of fulvestrant) and are observed within 28 days following the first dose of mirdametinib or patients who experience a DLT.
- **Efficacy Population**, used for the assessment of efficacy for each arm, will consist of all patients in Part 2 who received at least 1 dose of study drug and who have at least 1 post-baseline tumor assessment. Arms 1 and 2 will be analyzed separately. In addition, patients treated at the MTD in the dose escalation portion of the protocol (both arms 1 and 2) will be included in the efficacy analyses for the expansion cohorts in part 2 if they meet the requirements for efficacy population as defined above. Additionally, the RP2D will be determined pending the clinical data obtained in the dose escalation portion of the protocol. If the RP2D is less than the MTD, then patients treated at the RP2D in the dose escalation portion of the protocol (both arms 1 and 2) will be included in the

Memorial Sloan Kettering Cancer Center
[name]
[name]

efficacy analyses for the expansion cohorts in part 2 if they meet the requirements for efficacy population as defined above.

- **Pharmacokinetic Population**, used for the assessment of pharmacokinetic endpoints, will consist of all patients who have sufficient pharmacokinetic concentration data recorded to derive pharmacokinetic endpoints.
- **All treated population or safety population:** consisting of all patients who receive any amount of drug

Arms 1 and 2 will be analyzed separately throughout the study.

Arm 1

The study will follow a standard 3+3 dose escalation schema. As described previously in section 4.2, the 3+3 decisions in Part 1 of Arm 1 will be made starting with a mirdametinib starting dose level (4 mg BID PO), where subjects will be treated with mirdametinib 4 mg BID PO given continuously in combination with the recommended dose of fulvestrant. If ≤ 1 of the first 3 DLT evaluable subjects in Dose Level 1 exhibit a DLT in Cycle 1, then Dose Level 1 will be expanded. Mirdametinib dose in combination with fulvestrant will not be escalated above the 4 mg BID given continuously dose level.

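### ORR, CBR and PFS omit treated patients with no post-baseline scan, and no all-treated efficacy analysis is planned; the effect is modest and the fix is rewording

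*Combined protocol and SAP*

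**What the plan says.** Section 14.1 defines the Efficacy Population as Part 2 patients "who received at least 1 dose of study drug and who have at least 1 post-baseline tumor assessment". It adds certain Part 1 patients who meet the same conditions: "patients treated at the MTD in the dose escalation portion of the protocol (both arms 1 and 2) will be included", and those at the RP2D if that is lower.

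Section 14.5 bases the primary efficacy analyses on this set. For the two rates it says: "For ORR and CBR, patients without a post-baseline tumor assessment will be excluded as they are not efficacy evaluable". Of the PFS analysis it says: "This analysis will include the patients in the efficacy population". Yet PFS is defined as the time from Day 1 "to disease progression as defined by RECIST v1.1 criteria, or death from any cause".

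Section 14.1 also defines an all-treated or safety population, "consisting of all patients who receive any amount of drug". The plan uses it for safety (14.3) and baseline summaries (14.6), not for efficacy. The only efficacy sensitivity analysis named is an optional central review of images.

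On cohort size, section 4.2 says for Arm 1: "The following expansion treatment groups (up to 28 subjects each"; and for Arm 2: "One or more expansion cohorts (up to 30 subjects each) will be started". The sample-size text in 14.5 asks for 28 efficacy-evaluable patients in each of two cohorts per arm, with an enrollment goal of 60 per arm to allow for non-evaluable patients.

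**The concern.** Membership of the efficacy set depends on something that happens after treatment starts, namely surviving and staying in the trial long enough to be scanned. Those who do not are unlikely to be a random sample.

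- **ORR and CBR.** An unscanned patient can contribute to the denominator but never to the numerator. Removing that patient can only move the rate up or leave it at zero.
- **PFS.** The first scheduled scan is at about 8 weeks (section 13.4.2). A patient who dies unscanned before then has a PFS event by the plan's own definition, but is dropped from the curve. The analysis set contradicts the endpoint.
- **DOR.** It is unaffected, because it is defined only in confirmed responders.

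A reader could rebuild an all-treated ORR from the disposition counts in 14.6, but not the Kaplan-Meier estimates, which need the dates of the omitted deaths.

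The plan also does not settle whether unscanned patients are replaced. A cap of 28 subjects in an Arm 1 cohort leaves no room for replacement, while the target of 28 evaluable and 60 enrolled implies it. This matters because the error rates of the 5-response rule depend on how many patients are treated.

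**Working it through.** **Inputs.** From 14.5: null rate 10%, promising rate 25%, at least 5 responses of 28, stated type I error 14%, power 86%, per-arm family-wise error 26%; 56 evaluable from 60 enrolled per arm, or 28 from 30 per cohort. Assumptions: the 4 of 60 are treated but unscanned (section 9.0 places enrollment at consent, so some may never have been dosed), and the true 6-month PFS takes the values shown.

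**The plan's own figures.** By exact binomial, P(X ≥ 5; 28, 0.10) = 0.142 and P(X ≥ 5; 28, 0.25) = 0.865. From the stated 14%, 1 − (1 − 0.14)² = 0.26. All agree with the plan.

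**ORR, with Clopper-Pearson 95% intervals.**

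| Situation with 5 responders | As planned | All treated |
|---|---|---|
| 30 treated, 2 unscanned | 5/28 = 17.9% (6.1–36.9%) | 5/30 = 16.7% (5.6–34.7%) |
| 28 treated, 2 unscanned | 5/26 = 19.2% (6.6–39.4%) | 5/28 = 17.9% (6.1–36.9%) |

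**PFS, per arm.** Let d of the unscanned patients die before a scan, with 56 scanned and no other censoring before 6 months. The correct estimate S divides the 6-month survivors by 56 + d; the planned one divides them by 56. So reported S(6) = S × (56 + d)/56.

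| Correct 6-month PFS (assumed) | d = 1 | d = 2 | d = 4 |
|---|---|---|---|
| 20% | 20.4% | 20.7% | 21.4% |
| 30% | 30.5% | 31.1% | 32.1% |
| 50% | 50.9% | 51.8% | 53.6% |

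In a single cohort with 28 scanned, each death counts for more: 30% becomes 0.30 × 29/28 = 31.1% with one and 0.30 × 30/28 = 32.1% with two.

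For the median, assume an exponential curve with 30% at 6 months: rate = −ln(0.30)/6. The correct median is ln 2/rate = 3.45 months. The reported median, −ln(0.5 × 56/(56 + d))/rate, is 3.54 months for d = 1 and 3.63 for d = 2.

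Unscanned patients who are alive would be censored at Day 1. That leaves the Kaplan-Meier estimate as it is when they are excluded, so excluding them adds no bias.

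**Decision rule.** The rule counts responses, and the exclusion removes none. What can change is the number treated to reach 28 evaluable. If the 10% null refers to all treated patients:

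- 28 treated, all scanned: 14.2%. With 26 scanned, P(X ≥ 5; 26, 0.10 × 28/26) = 0.141.
- 30 treated, 28 scanned: P(X ≥ 5; 28, 0.10 × 30/28) = 0.175. Two cohorts: 1 − (1 − 0.175)² = 0.319, against the stated 26%.
- Larger unscanned shares (assumed), still with 28 evaluable: 19.4% at a 10% share, 22.8% at 15%, 26.8% at 20%.

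If the null refers to evaluable patients, 14% stands with 28 evaluable. Section 14.5 does not say which is meant.

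**The case against.** The strongest reply is that this is small, open and conventional. Response-evaluable sets are common in early-phase trials, and this one is pre-specified. The threshold ORR moves by 17.9 − 16.7 = 1.2 points, inside an interval of 6.1% to 36.9%. Few patients should be lost: section 6.1 requires ECOG 0 or 1 and a life expectancy of at least 3 months, section 13.4.2 allows earlier scans and continues them after discontinuation for toxicity or clinical progression, and Table 3 has an end-of-treatment assessment. Efficacy is secondary and the cohorts are called exploratory. Most of this stands and limits the weight of the point. It does not explain why deaths leave an endpoint that counts them, or why no all-treated analysis appears even as a sensitivity analysis. The plan also sets no limit on the unscanned share.

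A second reply is that the type I error figures above 14% rest on an all-treated null, whereas 14.5 speaks of 28 efficacy-evaluable patients. That is fair. Those figures are conditional and are not needed for the main point.

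A third is that the enrollment goal of 60 shows an intention to replace. It does, but it conflicts with the Arm 1 cap of 28, so the text still needs reconciling.

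Finally, censoring living, unscanned patients at Day 1 does not cure informative dropout. That is true, and the proposed change repairs only the omitted deaths.

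**Conclusion.** The concern holds and should be fixed, though it is not serious. The direction for ORR and CBR is certain: up or unchanged. PFS is biased upward by each early death that is dropped.

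On the assumption that about 2 patients per cohort are treated but unscanned, ORR at the threshold is overstated by 1.2 to 1.3 points. Per-arm 6-month PFS is overstated by 0.4 to 1.8 points for one or two dropped deaths, and by at most 3.6 points if all four unscanned patients died (over assumed true rates of 20% to 50%). A higher unscanned share would enlarge these figures.

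Type I error departs from 14% only if more than 28 are treated to reach 28 evaluable and the null refers to all treated patients; it is then about 17.5% per cohort and 32% per arm.

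**What to change.** - In 14.1 and 14.5, analyse ORR, CBR and PFS in all patients treated at the RP2D in the relevant cohort, including the Part 1 patients whom 14.1 already pools.
- Count patients without a post-baseline scan as non-responders and as without clinical benefit.
- In PFS, count death before the first scan as an event, and censor at Day 1 those alive without a scan.
- Keep the scan-evaluable set as a sensitivity analysis.
- State the n for the decision rule, whether unscanned patients are replaced (reconciling 28, 30 and 60 in sections 4.2 and 14.5), and whether pooled Part 1 patients count toward it.

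At least 5 of 28 treated keeps the plan's figures: 14.2% type I error and 86.5% power. If 30 are treated, the operating characteristics must be restated: at least 5 of 30 gives 17.5% and 90.2%; at least 6 of 30 gives 7.3% and 79.7%. Neither reproduces 14% and 86%, so that route is a design choice to be made openly.

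The cost is rewording of 14.1, 14.5 and the sample-size paragraphs, plus one stated n. The all-treated population is already defined, so no patients, visits or data are added. The downside is slightly lower reported ORR, CBR and PFS.
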